## APPENDIX A

**Procedure for Obtaining a Urine Protein:Creatinine Ratio** (Or alternatively calculate from the serum creatinine based on gender and age)

- 1) Obtain at least 4 ml of a random urine sample (does not have to be a 24 hour urine).
- 2) Determine protein concentration (mg/dL).
- 3) Determine creatinine concentration (mg/dL).
- 4) Divide #2 by #3 above:  $\text{urine protein} / \text{creatinine ratio} = \text{protein concentration (mg /dL)} / \text{creatinine concentration (mg /dL)}$ .

The UPC directly correlates with the amount of protein excreted in the urine per 24 hrs (i.e. a UPC of 1 should be equivalent to 1g protein in a 24hr urine collection).

Protein and creatinine concentrations should be available on standard reports of urinalyses, not dipsticks. If protein and creatinine concentrations are not routinely reported at an institution, their measurements and reports may need to be requested

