## **3.2 Exclusion Criteria**

**3.2.i.** Patients who have previously received IL-2 are not eligible. Patients on HCQ in neoadjuvant protocols or in the past for clinical indications ARE eligible, as are patients who have previously received CTLA-4 and/or PD-1/PD-L1 antibodies.

**3.2.ii.** Concomitant second malignancy except for non-melanoma skin cancer, and non-invasive cancer such as cervical CIS, superficial bladder cancer without local recurrence or breast CIS.

**3.2.iii.** In patients with a prior history of invasive malignancy, less than five years in complete remission.

**3.2.iv.** Positive serology for HIV, hepatitis B or hepatitis C

**3.2.v.** Significant co-morbid illness such as uncontrolled diabetes or active infection that would preclude treatment on this regimen.

**3.2.vi.** Use of corticosteroids or other immunosuppression (if patient had been taking steroids, at least 2 weeks must have passed since the last dose).

**3.2.vii.** History of inflammatory bowel disease or other serious autoimmune disease. (Not including thyroiditis and rheumatoid arthritis). Patients already on hydroxychloroquine for such disorders are not eligible.

**3.2.viii.** Patients with organ allografts.

**3.2.ix.** Uncontrolled hypertension (BP >150/100 mmHg).

**3.2.x.** Proteinuria dipstick > 3+ or  $\geq$  2gm/24 hours.

**3.2.xi.** Urine protein:creatinine ratio  $\geq$  1.0 at screening.

**3.2.xii.** Major surgery, open biopsy, significant traumatic injury within 28 days of starting treatment or anticipation of need for major surgical procedure during the course of the study.

- 3.2.xiii. Minor surgical procedures, fine needle aspirations or core biopsies within 7 days prior to starting treatment. Central venous catheter placements are permitted.
- 3.2.xiv. History of abdominal fistula, gastrointestinal perforation, or intraabdominal abscess within 6 months prior to starting treatment.
- 3.2.xv. Serious, non-healing wound, ulcer, or bone fracture.
- 3.2.xvi. History of tumor-related or other serious hemorrhage, bleeding diathesis, or underlying coagulopathy.
- 3.2.xvii. History of deep venous thrombosis, clinically significant peripheral vascular disease, or other thrombotic event.
- 3.2.xviii. Inability to comply with study and/or follow-up procedures.

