## 5.0 PRE-STUDY TESTING/STAGING

All patients considered for entry in the trial should have measurable or evaluable metastatic disease as described in the RECIST 1.1 criteria (see Section 11.0). Staging will include:

- 5.1 History and physical examination within two weeks of the first day of treatment (day -14).
- 5.2 Within 4 weeks prior to treatment (day -14), the following procedures are required:
  - 5.2.i CT scans of the chest/abdomen/pelvis
  - 5.2.ii Brain MRI or enhanced brain CT
  - 5.2.iii Bone scan (if clinically indicated)
  - 5.2.iv Cardiac stress test: All patients over 40 years of age or with significant cardiac history
  - 5.2.v Pulmonary function tests within 4 weeks of starting therapy for all patients over 50 years old or with significant pulmonary or smoking history
  - 5.2.vi Cardiac ECHO or MUGA scan to assess LVEF
  - 5.2.vii 12-lead EKG
- 5.3 Within 2 weeks prior to treatment (day -14) the following procedures are required:
  - 5.3.i Urine protein:creatinine ratio (see appendix A)
  - 5.3.ii Urinalysis
  - 5.3.iii Laboratory tests: HIV, hepatitis B and C serology, pregnancy test when indicated, CBC with differential, comprehensive metabolic panel (creatinine, BUN, albumin, total protein, glucose, electrolytes, liver function tests [total bilirubin, alkaline phosphatase, aspartate aminotransferase, alanine aminotransferase]), direct bilirubin, LDH, Ca, PO4, TSH, PT, PTT. A serum sample for determination of serum VEGF/ANG1/ANG2 levels will be drawn on day -14, prior to the dose of hydroxychloroquine.
- 5.4 Within 4 weeks after enrollment, tissue blocks or four unstained slides of renal tissue sent to central pathology facility.

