- e.** ECHO or MUGA will be performed at baseline. ECHO will be performed prior to start of each new course only if clinically indicated (section 10.3.3).
- f.** Screening labs to include CBC w/differential, CMP (creatinine, BUN, albumin, total protein, glucose, electrolytes [Na, K, Cl, HCO3], liver function tests [total bilirubin, ALP, AST, ALT]), direct bilirubin, calcium, phosphorus, LDH, TSH, PT, PTT, HIV, Hep B and C, Pregnancy test for women of childbearing potential.
- g.** Proteinuria level must be checked prior to each cycle of IL-2.
- h.** Outpatient labs to include CBC w/differential, CMP (creatinine, BUN, albumin, total protein, glucose, liver function tests [total bilirubin, ALP, AST, ALT], electrolytes [Na, K, Cl, HCO3]), LDH, CPK, amylase, and lipase.
- i.** Inpatient labs to include CBC w/differential, CMP (creatinine, BUN, albumin, total protein, glucose, liver function tests [total bilirubin, ALP, AST, ALT], electrolytes [Na, K, Cl, HCO3]), direct bilirubin, calcium, magnesium, phosphorus, LDH, CPK, amylase, and lipase.
- j.** Outpatient labs to include CBC w/differential, CMP (creatinine, BUN, albumin, total protein, glucose, liver function tests [total bilirubin, ALP, AST, ALT], electrolytes [Na, K, Cl, HCO3]), amylase, and lipase
- k.** Patients with no evidence of progression by RECIST 1.1 criteria may receive continued treatment with hydroxychloroquine through one year of initiation of HCQ treatment (Day -14) until disease progression.
- l.** IL-2 every 8 hours on days 1-5 (or 6) and 15-19 (or 20) (maximum 14 doses per 5 day cycle). Dependent upon when Dose 1 is administered on Day 1/Day 15, Dose 14 could require hospitalization on Day 6/Day 20.
- m.** HCQ daily dosing starting on Day -14 (minimum of 14 days, plus a window of + 7 days if needed)
- n.** See Table 6 for sampling schedule. Cycle 2 draws will only be done in Course 1.
- o.** Blocks or slides will be sent within 4 weeks after enrollment.
- p.** Subjects will be evaluated with physical examination ~30 days (28-42 days) after being removed from study for any reason.

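### Appendix A lets sites derive the urine protein:creatinine ratio from serum creatinine, sex and age, which cannot test exclusion 3.2.xi

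*Combined protocol and SAP*

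**What the plan says.** Two separate exclusions in Section 3.2 concern proteinuria. 3.2.x begins "Proteinuria dipstick > 3+ or" and continues with 2 g or more per 24 hours. 3.2.xi excludes a "Urine protein:creatinine ratio" of 1.0 or more, and applies that limit at screening.

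Section 5.3.i requires, within two weeks before day -14, a "Urine protein:creatinine ratio (see appendix A"). Urinalysis is a separate requirement (5.3.ii).

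Appendix A gives the procedure. Step 1 is "Obtain at least 4 ml of a random urine sample (does not have to be a 24 hour urine"), step 2 is "Determine protein concentration (mg/dL"), step 3 does the same for creatinine, and step 4 divides the first concentration by the second. Its heading adds, in parentheses, "Or alternatively calculate from the serum creatinine based on gender and age". Below the steps it gives a conversion: "a UPC of 1 should be equivalent to 1g protein in a 24hr urine collection".

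For later cycles, Appendix B footnote g, attached to the urinalysis row, says "Proteinuria level must be checked prior to each cycle of IL-2" and names no limit. Section 6.4.2 withholds therapy until laboratory values are back within the eligibility criteria.

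**The concern.** The parenthetical sits in the procedure that 5.3.i cites, so it reads as a permitted way to meet the requirement. A site following it would record a figure, or tick a box, for an exclusion that it had not assessed. Nothing in the protocol's wording would give the coordinating center's eligibility review (4.3) a reason to reject the result.

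What is at stake is a safety screen. Section 6.3.2.4 says that IL-2 is cleared and metabolised by the kidney. Section 6.3.2.5 lists proteinuria and glomerulonephritis among its toxicities, and 9.5.11 makes nephrotic syndrome a reason for no further therapy. If sites differ in the route they use, two patients with the same proteinuria could receive different entry decisions.

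**Working it through.** No sample size, power or error rate is involved. The check has three parts: what the alternative inputs can yield, how the two limits compare, and which decisions change.

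**1. What serum creatinine, sex and age can yield**

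Appendix A, step 4: UPC = urine protein (mg/dL) / urine creatinine (mg/dL).

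Hold a patient's serum creatinine, sex and age fixed and assume a urine creatinine of 100 mg/dL. The urine protein values are also assumed, and the last two columns use Appendix A's 1:1 conversion.

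| Urine protein (mg/dL) | UPC | Excluded by 3.2.xi (1.0 or more) | Excluded by 24-hour part of 3.2.x (2 g or more) |
|---|---|---|---|
| 10 | 0.10 | no | no |
| 50 | 0.50 | no | no |
| 99 | 0.99 | no | no |
| 100 | 1.00 | yes | no |
| 150 | 1.50 | yes | no |
| 200 | 2.00 | yes | yes |
| 400 | 4.00 | yes | yes |

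All seven patients look identical to the alternative route, yet they fall on both sides of the 3.2.xi limit.

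The most those inputs can support is a renal-function estimate, and the protocol's own formula for that (Cockcroft-Gault, 3.1.vi.c) also needs weight. Daily creatinine excretion follows from it:

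- Clearance (mL/min) = (140 − age) × weight × [0.85 if female] / (72 × serum creatinine).
- Excretion (mg/day) = clearance × serum creatinine × 1440 / 100 = 0.2 × (140 − age) × weight × [0.85 if female].

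Serum creatinine cancels. For assumed patients:

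- Woman, 75 years, 60 kg: 0.2 × 65 × 60 × 0.85 = 663 mg/day, about 0.66 g/day.
- Man, 40 years, 100 kg: 0.2 × 100 × 100 = 2000 mg/day, or 2.0 g/day.

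Both figures are creatinine, not protein. Even with weight added, the numerator of the UPC is missing.

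**2. The two limits on one scale**

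Appendix A equates UPC 1 with 1 g per 24 hours. The 24-hour limit in 3.2.x is therefore UPC 2.0, against 1.0 in 3.2.xi: 2.0 / 1.0 = 2.

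The factor is nominal. Dividing 2 g/day by the excretion figures above gives 2 / 0.663 = 3.0 for the woman and 2 / 2.0 = 1.0 for the man. Over these assumed patients, 2 g per 24 hours corresponds to a UPC between 1.0 and 3.0.

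**3. Which decisions change**

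Either exclusion is enough on its own.

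- UPC measured in urine: exclusion starts at UPC 1.0 under 3.2.xi, and the 2 g limit is in effect redundant.
- Alternative used: 3.2.xi is untested and only 3.2.x remains. Neither 5.3 nor Appendix B schedules a 24-hour collection, so in practice this means the dipstick limit. The documents do not convert that limit to grams.

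The nominal gap is 1 to below 2 g per 24 hours. Without a 24-hour result, a patient above that range is also caught only if the dipstick exceeds 3+.

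**The case against.** The strongest reply is that this is one stray phrase. It offers no formula, all the numbered steps call for urine, and the closing text of Appendix A tells sites to take the concentrations from urinalysis reports. Urinalysis is mandatory at screening, and external sites' eligibility documents are reviewed centrally. The phrase may be a creatinine-clearance note in the wrong place, although the documents do not say so. This reply lowers the likelihood of harm. It does not make the alternative valid.

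Four stronger readings are tempting, and the documents do not support them.

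- *A reader might infer that the twofold difference itself causes wrong entry decisions.* It does not. At 1.5 g per 24 hours, 3.2.xi excludes the patient whether or not 3.2.x does.
- *A reader might infer that the effective limit becomes 2 g per 24 hours wherever the alternative is used.* With no scheduled 24-hour collection and no gram equivalent for the dipstick, the effective limit is unknown.
- *A reader might infer that a serum-based figure compared with 1.0 would exclude nearly everyone, because eligible patients have clearances of 60 mL/min or more.* The units differ, and 3.1.vi.c also admits on serum creatinine of 1.5 mg/dL or less. The woman above with creatinine 1.5 has a clearance of 65 × 60 × 0.85 / (72 × 1.5) = about 31 mL/min and still meets that criterion.
- *A reader might infer that the primary estimate is compromised.* Section 11.0 does limit the main response analysis to eligible patients, but that is true of every criterion. It also has all included patients assessed for response, even if ineligible. No effect on the estimate can be quantified.

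**Conclusion.** The defect holds as written. Appendix A permits a route to the UPC that contains no urine protein, contradicts its own steps 1-4, and leaves 3.2.xi untested wherever it is used. The consequence is conditional: a patient whom 3.2.xi should exclude *can* enter, provided that a site uses the alternative and 3.2.x does not catch the proteinuria. The conclusion rests on reading the parenthetical as operative text, which the reference in 5.3.i supports.

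The size in patients is unknown. The documents neither show use of the alternative nor give the share of patients with UPC 1.0 or more. The twofold difference between limits rests on Appendix A's nominal conversion and matters only where no valid UPC was obtained. The point concerns eligibility and safety screening. It does not touch the sample size or the stopping rule.

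A smaller ambiguity remains for later cycles. 3.2.xi is tied to screening, 3.2.x is not, 6.4.2 refers back to the eligibility criteria, and footnote g gives no limit. Which measure and limit govern the pre-cycle check is therefore not stated.

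**What to change.** Delete the parenthetical from the Appendix A heading, so that only the urine measurement in steps 1-4 satisfies 5.3.i and 3.2.xi. If the phrase was meant for the creatinine-clearance criterion, that is already covered by 3.1.vi.c.

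Separately, the sponsor should reconcile 3.2.x, 3.2.xi, 6.4.2 and Appendix B footnote g, stating which proteinuria measure and limit apply at entry and which before later IL-2 cycles. No view is offered here on which limit is right.

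The deletion is a single wording edit and adds no procedure, because the UPC is already a required screening test. The reconciliation is a wording change once the sponsor has decided what was intended. If patients have already been screened, a check of source records would show whether any UPC was derived from serum creatinine.

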## APPENDIX B - Schedule of Events

Study Visit	Screening		Study start	Each Course (1-3)								End of Study Visit q	Follow Up r
	Days -41 to -14	Days -27 to -14	Day -14	Day 1	Days 7-14	Day 15	Day 29	Day 43	Day 57	Day 71	Day 84		
History/Physical exam		X	X	X		X	X		X			X	X
Concomitant medications	X	X	X	X		X	X		X			X	X
Adverse events	X	X	X-----X								X	X	
Radiologic exams	X a								X b		X		X b
Pulmonary Function Testing	X c												
Cardiac Stress Test	X d												
12-lead EKG	X												
ECHO or MUGA for LVEF	X e										X e		
Screening labs		X f											
Urine protein:creatinine ratio		X											
Urinalysis g		X		X		X							
Patient Registration		X											
Treatment labs			X h	X i	X j	X i	X h		X h, k				
IL-2 l				X l		X l							
Hydroxychloroquine m			X-----X k										
Research blood draws n			X	X		X n							
Pathology submission						X o							
Telephone contact for toxicity assessment					X								
Subject Drug Administration Diary for HCQ Tablets			X	X			X		X			X	X k

a. Within 4 weeks prior to day -14 patients will have CT scan of chest/abdomen/pelvis and brain MRI. If clinically indicated a bone scan should be done.
 
b. After week 8 (+/- 1 week) and week 12 (+/- 1 week) of each course patients will have CT of chest/abdomen/pelvis. If clinically indicated repeat bone scan and brain MRI. After the final course (week 36), patients will have CT scan evaluation every 12 weeks for up to one year or until tumor progression (whichever occurs first). For patients who have not shown progression at the end of one year, response will be captured during follow-up survival via telephone contact and medical record review. If additional scans are performed for clinical reasons, the study schedule may be altered to perform the requisite scans at a more acceptable time point. The change in timing of study scans must be approved by the local PI and documented.
 
c. All patients over 50 years of age or those with significant pulmonary or smoking history.
													

- d.** All patients over 40 years of age or with significant cardiac history.
- e.** ECHO or MUGA will be performed at baseline. ECHO will be performed prior to start of each new course only if clinically indicated (section 10.3.3).
- f.** Screening labs to include CBC w/differential, CMP (creatinine, BUN, albumin, total protein, glucose, electrolytes [Na, K, Cl, HCO3], liver function tests [total bilirubin, ALP, AST, ALT]), direct bilirubin, calcium, phosphorus, LDH, TSH, PT, PTT, HIV, Hep B and C, Pregnancy test for women of childbearing potential.
- g.** Proteinuria level must be checked prior to each cycle of IL-2.
- h.** Outpatient labs to include CBC w/differential, CMP (creatinine, BUN, albumin, total protein, glucose, liver function tests [total bilirubin, ALP, AST, ALT], electrolytes [Na, K, Cl, HCO3]), LDH, CPK, amylase, and lipase.
- i.** Inpatient labs to include CBC w/differential, CMP (creatinine, BUN, albumin, total protein, glucose, liver function tests [total bilirubin, ALP, AST, ALT], electrolytes [Na, K, Cl, HCO3]), direct bilirubin, calcium, magnesium, phosphorus, LDH, CPK, amylase, and lipase.
- j.** Outpatient labs to include CBC w/differential, CMP (creatinine, BUN, albumin, total protein, glucose, liver function tests [total bilirubin, ALP, AST, ALT], electrolytes [Na, K, Cl, HCO3]), amylase, and lipase
- k.** Patients with no evidence of progression by RECIST 1.1 criteria may receive continued treatment with hydroxychloroquine through one year of initiation of HCQ treatment (Day -14) until disease progression.
- l.** IL-2 every 8 hours on days 1-5 (or 6) and 15-19 (or 20) (maximum 14 doses per 5 day cycle). Dependent upon when Dose 1 is administered on Day 1/Day 15, Dose 14 could require hospitalization on Day 6/Day 20.
- m.** HCQ daily dosing starting on Day -14 (minimum of 14 days, plus a window of + 7 days if needed)
- n.** See Table 6 for sampling schedule. Cycle 2 draws will only be done in Course 1.
- o.** Blocks or slides will be sent within 4 weeks after enrollment.
- p.** Subjects will be evaluated with physical examination ~30 days (28-42 days) after being removed from study for any reason.
- q.** After the final course of treatment, follow-up procedures will be performed every 3 months (+/- 2 weeks) for up to one year or until disease progression (whichever occurs first). Follow-up procedures will include CT scan, routine laboratory tests, and physical examination. Subjects will then be followed for survival by telephone contact and medical record review every 3 months for one year following the time of disease progression or after one year off of treatment, then every 6 months for the next two years, then annually until death. A window of +/- 2 weeks is permitted.

If a subject's treatment and/or testing days need to be rescheduled due to the subject's inability to comply with the study calendar (i.e., hospitalizations, business and vacation travel plans, illness, transportation issues, holidays, family emergencies, etc.), a window of +/- one week is available for rescheduling of treatment and procedures per the discretion of the treating physician investigator, and as discussed with the principal investigator.

## Appendix C

### Blood Draw Instructions for Research Labs for Protocol IL-2HQ

#### A Phase II Study of Hydroxychloroquine and Aldesleukin in Patients with Advanced RCC

Comments	Treatment Day	Timepoint	Tube(s) to draw	Storage condition
Hydroxychloroquine is oral	Day -14	Pre-dose of Hydroxychloroquine	2 lge (10ml) Red top 10 lge (10ml) sod. Hep. Green top 1 PAXgene RNA blood tube (2.5ml)	1 on ice or in frig., 1 ambient 10 tubes at ambient temp. on their side 1 tube on ice or in frig
	Course 1 Cycle 1 Day 1 and 2	Please draw blood before pre-treatment ancillary medication is given Pre-dose of IL-2 (post-dose PO HCQ)	2 lge (10ml) Red top 10 lge (10ml) sod. Hep. Green top 1 PAXgene RNA blood tube (2.5ml)	1 on ice or in frig., 1 ambient 10 tubes at ambient temp. on their side 1 tube on ice or in frig
		Just prior to Dose 4 of IL-2 (+/- 1 dose)	1 lge (10ml) Red top	On ice or in frig.
	Course 1 Cycle 1 Day 15 and 16	Pre-dose of Hydroxychloroquine	2 lge (10ml) Green top 1 lge (10ml) Red top	Ambient temp. on their side On ice or in frig.
		just prior to Dose 4 of IL-2 (+/- 1 dose)	1 lge (10ml) Red top	On ice or in frig.
	Course 1 Between Days 60-80	During clinic visit	2 lge (10ml) Red top 10 lge (10ml) sod. Hep. Green top 1 PAXgene RNA blood tube (2.5ml)	1 on ice or in frig., 1 ambient 10 tubes at ambient temp. on their side 1 tube on ice or in frig
	Course 2 Cycle 1 Day 1	Pre-dose of IL-2 (post-dose PO HCQ)	2 lge (10ml) Green top 1 lge (10ml) Red top	Ambient temp. on their side On ice or in frig.
	Course 3 Cycle 1 Day 1	Pre-dose of IL-2 (post-dose PO HCQ)	2 lge (10ml) Green top 1 lge (10ml) Red top	Ambient temp. on their side On ice or in frig.

## APPENDIX D

### **Processing Specimens for RCC Study (hydroxychloroquine / Aldesleukin for RCC)**

**1 Large Red Top Tube(s) for Serum (Kept on ice):** Please carry out in laminar flow hood to keep serum sterile.

- After blood is drawn, invert tube several times to mix well. Send to UPCI IMCPL overnight.
- IMCPL Centrifuge for 10 minutes at 900g to 1000g to separate out serum.
- Aliquot serum into prelabeled sterile freeze vials at approximately 0.5 to 1.0 ml per vial (4 vials maximum).
- Fill in vial labels with patient ID# and date. (Please be careful to use appropriate lettered vials)
- Fill in Inventory/Shipping Log for W0454
- Store vials at -70 to -80°C until ready to ship.

**1 Large Green Top Tube for Plasma (Kept on ice):** UPCI/IMCPL will carry out in laminar flow hood to keep plasma sterile.

- After blood is drawn, invert tube several times to mix well.
- Centrifuge for 10 minutes at 900g to 1000g to separate out plasma.
- Aliquot plasma into prelabeled sterile freeze vials at approximately 0.5 to 1.0 ml per vial (4 vials maximum).
- Fill in vial labels with patient ID# and date. (Please be careful to use appropriate lettered vials)
- Fill in Inventory/Shipping Log for IL-2HQ
- Store vials at -70 to -80°C until ready to ship.

**1 10cc Red Top Tube for Serum (kept at ambient temp.) AND  
10 Large Sodium Heparin Green Top Tubes for PBMCs. (Kept at ambient temp.):**

Batch specimens from one patient and ship on dry ice along with a copy of the Inventory / Shipping Log, for next day morning delivery by FedEx on a Monday-Thursday to:

Please call or e-mail to alert us of shipment arrival, including tracking number.

UPCI – IMCPL  
[name]  
